371 their baseline body weight and approximately 30% lost greater than 10% of their body weight.
372 These changes were significantly greater than weight loss seen in the placebo arms of these
373 three trials. In study 3 there were a statistically greater number of patients randomized to
374 placebo that gained at least 0.5% of their body weight at week 56. Liraglutide use was also
375 associated with a reduction in waist circumference, blood pressure and modest reductions in
376 total cholesterol, LDL and increase in HDL. Liraglutide was associated with an increase in heart
377 rate of approximately 2 beats per minute.

378
379 *Tolerability and Adverse Events*

380 Treatment with liraglutide in prior obesity trials was generally well tolerated. Approximately 70%
381 of patients randomized to liraglutide completed the trials on medication. The withdrawal rate
382 was approximately 8.5% in the liraglutide arms and 8.6% in the placebo treated patients.
383 Serious adverse events were relatively uncommon, but were more frequent in liraglutide-treated
384 subjects compared with placebo (4.2 vs. 2.4%). GI side effects seen in the SCALE
385 Maintenance trial were common in patients taking liraglutide 3.0 mg. The frequency of nausea
386 was 47.6%, of diarrhea was 17.9%, of constipation was 26.9% and of vomiting was 16.5%.
387 Other less common AEs included dyspepsia (9.4%), abdominal pain (6.6%), abdominal
388 distension (6.1%), eructation (5.2%), and flatulence (5.2%).²⁰

389
390 There have been rare, spontaneous post-marketing reports of acute pancreatitis in patients
391 without a history of pancreatitis being treated with liraglutide. In the obesity clinical trials, acute
392 pancreatitis was confirmed in 9 of 3291 liraglutide treated patients and 1 of 1843 placebo
393 treated patients. There were 3 additional cases of pancreatitis occurring in liraglutide treated
394 patients ranging 14 to 124 days after study discontinuation. A history of pancreatitis was an
395 exclusion criterion in clinical trials performed to date. If the investigator suspects acute
396 pancreatitis, all suspected drugs should be discontinued until confirmatory tests have been
397 conducted and appropriate treatment initiated.

398
399 Liraglutide causes dose-dependent and treatment-duration-dependent thyroid C-cell tumors at
400 clinically relevant exposures in both genders of rats and mice. It is unknown whether liraglutide

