597 2. Participants can be withdrawn from the trial at the discretion of the Investigator due to
 598 safety concerns of if judged to be non-compliant with the trial protocol.

599 3. Pregnancy or intention of becoming pregnant

600 4. If target treatment dose of the randomized product is not tolerated by the subject.

601 5. If the trial investigator suspects acute pancreatitis, the trial drug will be discontinued until
 602 the confirmatory tests (clinically indicated laboratory and imaging) have been conducted
 603 and appropriate treatment has been administered. We anticipate confirmation within 72
 604 hours. If acute pancreatitis is confirmed, the participant will be withdrawn from the trial.
 605 If acute pancreatitis is not confirmed, the participant will resume the trial drug at the
 606 same dose previously used before temporary discontinuation.

607 6. Temporary trial drug discontinuation criteria:
 608 - Side effects to trial medication (until such side effects have resolved or have
 609 been otherwise addressed)
 610 - Acute illness requiring treatment or hospitalization
 611 - The longest time that the subject can be off trial drug and still continue in the trial
 612 is 4 weeks. If the trial drug is discontinued for >72 hours, then the dosing
 613 escalation regimen will be restarted at 0.6 mg daily and titrated up according to
 614 prescribing information recommendations.

616 **Subject Replacement**

617 Participants will not be replaced if they withdraw or become ineligible but they will be asked to
 618 return at the end of the trial period to complete the follow-up imaging/laboratory testing and
 619 analyzed in an intention to treat analysis. As up to a 28% drop-out rate is anticipated, enrolment
 620 will account for expected drop-out to minimize loss to follow-up given that subjects will not be
 621 replaced.

623 **Rationale for Trial Population**

624 The trial population represents the target population for which liraglutide is approved for chronic
 625 weight management in adult patients, with the additional inclusion criterion of a diagnosis of
 626 metabolic syndrome. This important criterion has been selected to enrich the trial population
 627 with participants with a high visceral adipose tissue burden in order to improve the statistical
 628 power to observe a meaningful effect on visceral adipose mass and enrich the trial population
 629 with individuals at high risk for cardiovascular disease.

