809 Background medication should be withheld on the day of the fasting Visits 1, 3, and 16 until
 810 blood sampling has been done. At all other visits the background medication and trial product
 811 should be taken as usual during the conduct of the trial.

812

813 Trial product will be dispensed at visits 3 through 15. Subjects will be asked to bring all empty,
 814 partly used and unused trial product at visits 4 through 16 for drug accountability. The
 815 computerized randomization system should be contacted for trial product dispensing. If the
 816 subject attends the clinic for a visit not described in the protocol, then an Unscheduled Visit
 817 Form must be completed. The Unscheduled Visit Form should not be completed if the sole
 818 purpose of the visit is trial product dispensing. If an unscheduled visit is made for the purpose of
 819 dispensing trial products to the subjects then an unscheduled dispensing session must be
 820 completed in the computerized randomization system. If it is not possible to attend the visit
 821 within the visit window, the subjects should be called in for an Unscheduled Visit.

822

823 In case a subject is being prematurely withdrawn from the trial before or at visit 16, the
 824 Investigator will ensure that the procedures for the End of Treatment visit (Visit 16) are

825 undertaken, if possible. The primary reason (adverse event, non-compliance with protocol or
826 other) for discontinuation will be specified in the CRF and a computerized randomization system
827 withdrawal session should be completed. Even if the subject is not able to attend a final visit, the
828 End of Trial Form (EOT) must be completed.

829
830 Subjects that have discontinued the trial prematurely before Visit 16 will be asked to attend a
831 visit (Visit 16x) taking place 40 weeks after the randomization date. The purpose of this visit will
832 be recording of all outcome assessments if possible. If the subject is not willing to attend Visit
833 16x, it should be documented in the patient medical record that the subject has refused to
834 attend the visit.

835
836 **Visit 1**
837 At Visit 1, the informed consent will be reviewed again for signature and participants will be
838 screened for eligibility in the trial. This will include interview assessment for inclusion and any
839 exclusion criteria and laboratory components of the metabolic syndrome. Subjects that meet all

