1167 temperature must be kept. Storage facilities will be checked frequently (at least once every
1168 working day).

1169
1170 No trial product(s) should be dispensed to any person not enrolled in the trial and the
1171 computerized randomization system should always be updated when dispensing trial product(s).
1172 Returned trial product(s) (partly used or unused including empty packaging material) must be
1173 stored separately from non-allocated trial product(s) until the monitor has performed drug
1174 accountability. The monitor will be responsible for retrieval of trial products from the site.
1175 Destruction of trial products will be done according to local laws and will be recorded on a
1176 Destruction Form, which will be signed by the person responsible for destruction, as agreed with
1177 the monitor.

1178
1179 **Randomization and Blinding**

1180 Trial participants and investigators will be blinded to treatment allocation throughout the trial.

1181

1182 **Randomization Scheme:**

1183 Participants will be randomly assigned using a computerized randomization code generated by
1184 UT Southwestern.

1185

1186 **Breaking of Blinded Codes**

1187 Blinding codes will be broken at the end of the trial. Blinding codes will only be broken before
1188 the end of trial if a subject develops a serious adverse event requiring knowledge of the
1189 treatment allocation. At such time, the subject will be considered to have completed the trial and
1190 will not undergo any further trial treatment but may be asked to undergo assessment of trial
1191 endpoints when feasible. Whenever a code is broken, the person breaking the code must print
1192 the Code Break Confirmation generated by the computerized randomization system, record the
1193 reason, and sign and date the document. If the subject should be withdrawn following a code
1194 break, a withdrawal session should be completed in the computerized randomization system.

1195

1196 **CONCOMITANT ILLNESSES AND MEDICATIONS**

1197 All concomitant illnesses and medications will be recorded in the CRF and assessed as AEs or
1198 not AEs. If a subject is prescribed a medication meeting criteria for withdrawal/exclusion, the
1199 subject will have the opportunity to decide whether to take such medication and withdraw from
1200 the trial or not take it and continue the trial.

SUBJECT SAFETY AND DATA MONITORING**ADVERSE EVENTS:****Definitions****Adverse Event (AE):**

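### A subject unblinded for a serious adverse event is labelled as having completed the trial although treatment stops, and the week-40 endpoint request becomes optional and undated

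*Protocol*

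**What the plan says.** All places are in the Protocol.

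- **Breaking of Blinded Codes.** Early code-breaking is reserved for an SAE that requires knowledge of "treatment allocation. At such time, the subject will be considered to have completed the trial and" (the sentence continues) "will not undergo any further trial treatment but may be asked to undergo assessment of trial" "endpoints when feasible. Whenever a code is broken, the person breaking the code must print" a confirmation. A withdrawal session follows only if withdrawal is called for: "reason, and sign and date the document. If the subject should be withdrawn following a code" break.
- **Visit Procedures.** "Subjects that have discontinued the trial prematurely before Visit 16 will be asked to attend a" "visit (Visit 16x) taking place 40 weeks after the randomization date. The purpose of this visit will" be to record all outcome assessments if possible. For premature withdrawals at or before Visit 16, this section also requires the primary reason for discontinuation in the case record form. Adverse event is one of the listed reasons.
- **Subject Replacement.** "Participants will not be replaced if they withdraw or become ineligible but they will be asked to" come back at the end of the trial period for imaging and laboratory tests, and they are analysed by intention to treat.
- **Sample Size Calculation.** The target is at least 128 subjects who complete the full protocol. The 28% allowance is for subjects who stop trial medication.
- **Premature discontinuation.** End-of-trial imaging is offered to a subject who terminates early only if at least 40 weeks of treatment have been completed.

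**The concern.** A subject whose treatment ends early for safety is a treatment discontinuer. The code-break rule gives that subject the opposite status. The request for a week-40 visit, and the duty to record why the subject stopped, are both attached to premature discontinuation or withdrawal. A subject deemed to have completed does not literally meet either condition. In place of a firm request at a fixed time, the rule offers an optional assessment at an unspecified time.

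The primary endpoint is the percent change in visceral fat at 40 weeks, analysed by intention to treat. That analysis needs the week-40 MRI in subjects who stopped treatment. Those affected here are selected by an event after randomization that treatment may influence, so a missing scan cannot be assumed to be missing at random. The statistical analysis plan can say how to handle a missing MRI, but it cannot recover one that was never requested.

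**Working it through.** **1. The plan's own figures.** Inputs from Sample Size Calculation and Statistical Methods: difference 8 percentage points, SD 16, two-sided alpha 0.05, power 80%, allocation 1:1, 28% stopping medication.

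- Normal approximation: n per arm = 2 × (1.96 + 0.842)² × 16² / 8² = 2 × 7.85 × 4 = 62.8, so 63 per arm and 126 in total.
- Two-sample t-test: 64 per arm, 128 in total, power 80.1%. This matches the stated 128.
- Inflation: 128 / (1 − 0.28) = 177.8, so 178. This also matches. The allowance is 178 − 128 = 50 subjects.

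The sample size is not in dispute. The step shows that the plan budgets for stopped medication inside those 50, which is where a subject taken off treatment after a code break belongs.

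**2. The rules side by side for such a subject.**

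- *Status:* completed (Breaking of Blinded Codes), against one of those who stop medication (Sample Size Calculation).
- *Strength of the endpoint request:* may be asked, against will be asked (Visit Procedures, Subject Replacement).
- *Timing:* when feasible, against 40 weeks after randomization (Visit Procedures) or the end of the trial period (Subject Replacement).
- *Reason for stopping:* not mentioned in the code-break rule except through an optional withdrawal session, against required for premature withdrawals (Visit Procedures).
- *Imaging:* under Premature discontinuation, an early terminator with less than 40 weeks of treatment is not offered it at all. This disagrees with Visit Procedures and Subject Replacement for every early leaver, not only for those unblinded.

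**3. How many subjects.** Tolerability and Adverse Events reports that SAEs in earlier obesity trials were more frequent in liraglutide-treated "subjects compared with placebo (4.2 vs. 2.4%). GI side effects seen in the SCALE" programme are described next. Assume that these rates apply here, with 178 / 2 = 89 per arm:

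- Liraglutide: 89 × 0.042 = 3.7 expected.
- Placebo: 89 × 0.024 = 2.1 expected.
- Total: 5.9. Difference between arms: 1.6.

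Only SAEs that need a code break count, and the Protocol gives no share. With a share from 0% to 100%, the expected number affected is 0 to about 6 of 178.

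**4. Effect on power at the extreme.** Suppose that all 6 were counted within the 128 and all lacked week-40 data. The analysed number would be 128 − 6 = 122, and t-test power at a standardized difference of 8 / 16 = 0.5 would fall from 80.1% to 78.2%.

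**The case against.** The strongest reply is that the label is clumsy but that little follows from it. Much of this stands, and it rules out four stronger readings that a reader might infer.

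- *That these subjects are removed from Visit 16x.* No section excludes them. The code-break sentence keeps endpoint assessment open, and the section provides for a withdrawal session, which could bring in the Visit Procedures rules, including the reason for stopping and the week-40 request. What can be said is that the request is not clearly triggered.
- *That they count toward the 128.* That target is for subjects who complete the full protocol, and someone whose treatment stopped early need not be counted. Evaluability of Subjects defines a full analysis set and a safety set but no completer set, and it does not tie per-protocol membership to the code-break label. Disposition tables and per-protocol criteria may properly sit in the analysis plan, which is not at hand.
- *That an MRI taken at unblinding would enter as the end-of-trial value.* The endpoints are set at the end of 40 weeks of treatment. Early end-of-treatment procedures already apply to every premature withdrawal, so this risk is not special to the code-break rule.
- *That the bias runs one way by arm, with 3.7 and 2.1 as ceilings.* They are expected counts under rates from other trials. Placebo subjects are affected too, the code-break share is unknown, and the number could be zero.

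It is also fair to say that treating these subjects like other discontinuers settles little while Premature discontinuation restricts imaging. The fix has to cover that section too.

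The reply leaves the core untouched: the status is wrong by the Protocol's own use of the terms, and the endpoint request is weaker than, and not timed like, the one made to other early leavers.

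**Conclusion.** The point holds as an internal inconsistency with a small effect. Followed as written, the code-break rule gives a treatment discontinuer the status of having completed the trial. It also makes the week-40 primary endpoint optional and undated for that subject, in a trial whose primary analysis is by intention to treat.

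The size rests on two assumptions: that SAE rates from earlier trials carry over, and that the unstated code-break share lies somewhere between none and all. Even at the upper end, the loss is about 2 percentage points of power. The reason to act is the kind of missing data rather than the amount: it is tied to a safety event and may be unequal by arm, though the Protocol does not establish by how much or in which direction.

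**What to change.** 1. In Breaking of Blinded Codes, leave the instruction on trial treatment as it is. Replace the statement that the subject has completed the trial with a status of discontinued trial product, with adverse event recorded as the reason.
2. State there that the existing Visit 16x request, 40 weeks after randomization, applies to these subjects, so that their outcomes can enter the intention-to-treat analysis.
3. Reconcile this section with Subject Replacement, Sample Size Calculation and Visit Procedures, so that completion, discontinuation of treatment and withdrawal from the trial are used in the same sense throughout.
4. Reconcile Premature discontinuation with Visit Procedures and Subject Replacement on who is offered end-of-trial imaging. Without this, step 2 does not secure the week-40 MRI.

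The cost is a short wording amendment. No visit is added to the schedule, since Visit 16x already exists. The only extra work is the week-40 assessment in the few subjects affected who agree to attend.

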 563 9. Current or history of treatment with medications that may cause significant weight
 564 gain, within 1 month prior to screening for this trial, including systemic corticosteroids
 565 (except for a short course of treatment, i.e., 7- 10 days), tri-cyclic antidepressants,
 566 atypical antipsychotic and mood stabilizers (e.g., imipramine, amitriptyline,
 567 mirtazapine, paroxetine, phenelzine, clorpromazine, thioridazine, clozapine,
 568 olanzapine, valproic acid and its derivatives, and lithium).
 569 10. Diet attempts using herbal supplements or over-the-counter medications within 1
 570 month prior to screening for this trial.
 571 11. Current participation in an organized weight reduction program or within the last 1
 572 month prior to screening for this trial.
 573 12. Participation in a clinical trial within the last 3 months prior to screening for this trial.
 574 13. Familial or personal history of multiple endocrine neoplasia type 2 or familial
 575 medullary thyroid carcinoma.
 576 14. Personal history of non-familial medullary thyroid carcinoma.
 577 15. History of Major Depressive Disorder within the last 2 years.
 578 16. History of other severe psychiatric disorders, e.g., schizophrenia, bipolar disorder.
 579 17. Any lifetime history of a suicide attempt.
 580 18. A history of any suicidal behavior in the last month prior to randomization.
 581 19. Surgery scheduled for the trial duration period, except for minor surgical procedures,
 582 at the discretion of the Investigator.
 583 20. Known or suspected hypersensitivity to trial product(s) or related product(s).
 584 21. Known or suspected abuse of alcohol or narcotics.
 585 22. Language barrier, mental incapacity, unwillingness or inability to understand.
 586 23. Females of childbearing potential who are pregnant, breast-feeding or intend to
 587 become pregnant or are not using adequate contraceptive methods. These include
 588 abstinence and the following methods: diaphragm with spermicide, condom with
 589 spermicide (by male partner), intrauterine device, sponge, spermicide, Norplant®,
 590 Depo-Provera® or oral contraceptives.

591

592 **Withdrawal Criteria:**

593 1. Participants may withdraw at will at any time.
 594 - Informed consent may be withdrawn at any time.

595 - Permission to follow up for endpoint determination may be withdrawn at any time
 596 - This is distinguished from withdrawal of trial medication.

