631 **Imaging Assessments**

632 The primary and secondary endpoints of visceral fat, abdominal subcutaneous fat, lower body
 633 fat, liver fat, and total body fat and fat-free (lean) mass will be assessed using a Phillips 3T MRI
 634 system utilizing a two point Dixon fat-water segmentation technique (Advanced MR Analytics,
 635 Sweden).²¹ This MRI system has been extensively studied and validated in multiple cohorts,²¹⁻²³
 636 has excellent test/retest precision and reliability,²⁴ and is rapid (<6 minutes) and therefore cost
 637 effective.

638 **STATISTICAL CONSIDERATIONS:**

641 **Sample Size Calculation:**

642 This trial is powered to detect a clinically meaningful difference in the placebo-corrected relative
 643 reduction in VAT. The estimates used in the sample size calculations below are derived from

644 prior data from the SCALE program. Assuming a mean 8% relative reduction of VAT among
 645 placebo treated subjects and an expected 16% relative reduction of VAT among liraglutide
 646 treated subjects (with a standard deviation of 16%, based on data from [2]), we expect to require
 647 128 total subjects (in a 1:1 trial drug:placebo randomization scheme) to achieve 80% power to
 648 detect an 8% difference between groups at an alpha level of 0.05. Assuming an estimated 28%
 649 of subjects may withdraw trial medication during the trial, we expect a planned total of 178
 650 patients will be randomized in order to achieve at least 128 completers of the full trial protocol.
 651

Placebo-corrected Effect Size	Power		
	80%	85%	90%
Sample Size (Total N, 1:1 randomization)			
5%	322	368	432
8%	128	146	170
10%	82	92	108

652
 653 **Statistical Methods:** A formal statistical analysis plan will follow. Briefly, baseline
 654 characteristics between liraglutide and placebo treated groups will be compared using
 655 appropriate parametric or non-parametric tests depending on the distribution of the data. The
 656 primary outcome will be analyzed using an intention to treat analysis. Mean change in outcome
 657 measurements will be compared between groups using the appropriate statistical test.
 658 Outcomes will also be analyzed by subgroups including age (above/below median), sex, race
 659 (non-Hispanic black, non-Hispanic white, and Hispanic), BMI category (overweight, class I
 660 obese, class II/III obese), and prediabetes status (yes/no). In order to minimize type II error in

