 661 subgroup analyses by race, we will attempt to ensure Hispanics comprise at least 25% of the
 662 trial population. A pre-specified analysis stratified by those who did vs. did not lose $\geq 4\%$ body
 663 weight at 16 weeks of treatment will be performed prior to unblinding to determine differential
 664 outcomes among “responders” vs. “non-responders” as outlined in the package insert. All
 665 statistical tests are two-sided at a 5% significance level.
 666

667 **Interim Analysis:** No interim analysis will be performed.
 668

669 **Missing Data:** The preferred approach to missing data is to incorporate proactive standard
 670 operating procedures to mitigate the likelihood of missingness. We will implement measures to
 671 reduce missing data (both baseline and endpoint). The statistical analysis plan will describe
 672 analytical approaches to address missingness of data, including multiple imputation including
 673 the last observation carried forward (LOCF) and mixed-effects model repeated measure
 674 approaches. Sensitivity analyses will also be performed to determine the effect of missingness
 675 on the primary and secondary outcomes.
 676

DATA HANDLING AND RECORD KEEPING:

677 Subjects will be assigned an identification code. A subject's name and code will be contained
 678 within a small notebook and will be kept in a locked cabinet in the research coordinator's locked
 679 office. The research chart will contain personal health information and will be kept in locked file
 680 cabinet in the research coordinator's locked office. All other data on a computer will be de-
 681 identified with the subject's identification code. Blood samples waiting for analysis will not be
 682 labeled with the subject's name, but with the assigned identification code. The trial database will
 683 be password protected. No data will be sent over the internet unless it is encrypted. All email
 684 with subject-identifiable information will be password protected. Only key personnel will have
 685 access to the information in the trial database on an as-needed basis. Key personnel may not
 686

687 alter the data in the database or directly view all of it without specific cause and approval of the
688 PI.

689

690 **ETHICS:**

691

692 **Informed Consent**

693 Before screening takes place subjects will be provided with written and verbal information about

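### The Premature discontinuation section withholds the end-of-trial MRI from early leavers, whom two other Protocol sections ask to have it

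*Protocol*

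**What the plan says.** Five parts of the Protocol bear on what happens to a subject who leaves early.

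- **Premature discontinuation.** A subject who chooses to end the trial early attends a visit for body weight, adverse events and a discussion of end-of-trial imaging. Imaging for the primary and secondary endpoints is then offered on condition that the subject has had a minimum of 40 weeks on trial treatment.
- **Subject Replacement.** Participants who withdraw or become ineligible are not replaced, but are asked to "return at the end of the trial period to complete the follow-up imaging/laboratory testing and" be analysed by intention to treat.
- **Visit Procedures.** For a subject withdrawn before or at Visit 16, the Visit 16 procedures are to be done if possible. Those who left before Visit 16 are also asked to attend Visit 16x, timed at 40 weeks from randomization, to record the outcomes if possible. No minimum time on treatment is set.
- **Withdrawal Criteria.** Item 1 separates withdrawal of consent, or of permission for endpoint follow-up, from stopping drug: "This is distinguished from withdrawal of trial medication". Item 6 caps a treatment gap: "The longest time that the subject can be off trial drug and still continue in the trial" is 4 weeks.
- **Concomitant Illnesses and Medications.** If an excluded medicine is prescribed, the "subject will have the opportunity to decide whether to take such medication and withdraw from" "the trial or not take it and continue the trial".

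**The concern.** The primary endpoint is the percent change in visceral adipose tissue at week 40. The assessment schedule has MRI at baseline and at Visit 16 and nowhere between. A subject who leaves early and has no final scan therefore has no post-baseline value of the primary endpoint at all, only interim measures such as weight.

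The Protocol commits to intention to treat for the primary outcome, and Subject Replacement and Visit 16x are the means of delivering it. Premature discontinuation cuts across both with a condition that early leavers cannot meet. Staff who apply that section would not offer the scan; staff who apply Visit Procedures would. Where it is not offered, the observed data are those of subjects who stayed on treatment, and whatever method is used for missing data has to supply the rest. Reasons for leaving may differ between arms, since gastrointestinal side effects of liraglutide are expected to be common, so the missingness cannot be assumed harmless.

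**Working it through.** **Can an early leaver meet the condition?**

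Inputs: 40 weeks on treatment (Trial type); Visit 7 = week 4, Visit 10 = week 16, Visit 13 = week 28, Visit 16 = week 40 (Visit Schedule); no trial drug after Visit 16 (Visit 16).

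Shortfall = 40 − week of leaving:

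| Leaves at | Shortfall against 40 weeks |
|---|---|
| Week 4 | 36 weeks |
| Week 16 | 24 weeks |
| Week 28 | 12 weeks |

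The shortfall closes only at week 40, which is Visit 16 itself. Those who can satisfy the condition have reached the visit at which the scan is scheduled anyway. For everyone else the offer is empty.

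**Does any reading reconcile the sections?**

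| Reading of Premature discontinuation | What it conflicts with |
|---|---|
| It governs imaging at week 40 | Visit 16x, which asks early leavers for outcome assessments with no minimum treatment, and Subject Replacement, which asks them back for imaging |
| It governs only imaging at the discontinuation visit | Visit Procedures, which asks for Visit 16 procedures at withdrawal; Visit 16 includes imaging |

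Both readings leave a conflict.

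**How many subjects does this concern?**

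The Protocol's own figures reproduce. With a difference of 8, SD 16, two-sided 5% and 80% power, the normal approximation gives 2 × (1.960 + 0.842)² × (16/8)² = 62.8, so 63 per arm (126). The two-sample t-test gives 64 per arm, which is the stated 128. Allowing for 28%: 128 / (1 − 0.28) = 177.8, so 178.

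Sample Size Calculation assumes that 28% "of subjects may withdraw trial medication during the trial, we expect a planned total of 178" randomized. 0.28 × 178 = 49.8, about 50, and 178 − 50 = 128.

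So roughly 50 subjects are planned to stop trial medication, the group from which early leavers would mostly come.

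**Does the sample size change?**

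No. The 128 are completers of the full protocol, so the calculation already treats the other 50 or so as contributing nothing. Losing their scans leaves the stated power where it is. What changes is which subjects have an observed primary endpoint.

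**The case against.** **On the imaging condition.** Visit Procedures only asks, and only if possible, so no scan is guaranteed to early leavers. That is right as far as it goes, but those words allow for refusal or infeasibility; they do not introduce a treatment-duration bar. It can also be said that two sections agree and one is the outlier, which suggests a drafting slip; perhaps 40 weeks since randomization was meant. That is plausible and would resolve the conflict, but the text counts weeks of treatment and staff will read it so.

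**On the medication rule.** A reader might infer that a subject who takes an excluded medicine loses outcome follow-up. The documents do not support that: Subject Replacement and Visit 16x cover such a subject like any other who withdraws. A reader might also see an unprotected safety hazard. The subject remains free to take the medicine, and item 2 of the Withdrawal Criteria gives a safety route: "Participants can be withdrawn from the trial at the discretion of the Investigator due to" safety concerns. Premature discontinuation itself commits to every effort to ascertain adverse events in early leavers. What is left is a preference for keeping such subjects on interim visits.

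**On the responder analysis.** One might infer damage to the analysis by weight loss, where the stratification by "weight at 16 weeks of treatment will be performed prior to unblinding to determine differential" outcomes depends on Visit 10. It is defined by weeks on treatment, so a subject who had already stopped drug would not clearly belong in it, and missing data there may be handled in a SAP not at hand.

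**On size.** One might take 50 as an upper bound, or expect power to fall below 80%. Neither follows. The 28% is a planning estimate of stopping medication, whereas the imaging condition applies to subjects who opt to end the trial early; the two groups need not coincide. The Tolerability and Adverse Events section reports about 70% of liraglutide subjects completing earlier trials on medication, so 28% is no ceiling. A fall in power would need losses beyond the 28%, for which the Protocol gives no figure.

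**Conclusion.** The contradiction is real and sits in Premature discontinuation. Its treatment condition cannot be met by anyone leaving before Visit 16, and it conflicts with Subject Replacement and Visit Procedures on either available reading.

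It matters because the final scan is the only post-baseline measurement of the primary endpoint. If sites follow the condition, early leavers have none, and the intention-to-treat analysis rests on completers plus whatever is assumed about the others. The planning figure for subjects stopping medication is about 50 of 178. How many would actually lose a scan depends on which section sites follow and how many would have attended Visit 16x, and neither is known from the Protocol. The direction and size of any bias cannot be stated. Sample size and stated power stand.

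The excluded-medicine rule and the 4-week limit are secondary: their wording could say more plainly that leaving treatment is not leaving outcome follow-up, but they do not by themselves put the primary endpoint at risk.

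**What to change.** **Main change.** In Premature discontinuation, delete the condition on weeks of treatment. State that every subject who stops early is offered the week-40 MRI and laboratory assessments (Visit 16x), unless permission for follow-up is withdrawn.

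**Optional clarification.** In Concomitant Illnesses and Medications and in item 6 of the Withdrawal Criteria, state that withdrawing for these reasons ends trial drug and not outcome follow-up, in line with the distinction already drawn in item 1.

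**Cost.** A short wording amendment. Visit 16x already exists, and the scans are ones that two sections already request. Some subjects will be scanned while off drug or on a medicine that affects weight, which the commitment to intention to treat already accepts.
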